### PROCEDURES INVOLVED:

Study Design:

[figure not shown]
Treatment, Parallel Assignment, Double Blind (Subject, Caregiver, Investigator, Outcomes Assessor), Randomized, Efficacy Study.

Over the course of the study, subjects will participate in a therapy regimen involving either active practice of hand and arm movements or passive stretching of the digits, while concurrently receiving either cyproheptadine or placebo. Thus, the study has two experimental factors: Drug (cyproheptadine hydrochloride/placebo) and rehabilitative movement training (active/passive). Subjects will be randomly divided into four groups, stratified by initial FMA score, consisting of the four combinations of Drug and Training:

- cyproheptadine with active movement training
- placebo with active movement training

- cyproheptadine with passive stretching
- placebo with passive stretching.

Twenty-five subjects in each group will complete the study for a total of 100 participants. The therapists, other research personnel (including the PI), and the subjects will all be blinded as to which agent each subject is taking.

**Fig. 2**. Dosage and evaluation scheduling for the subjects. During the titration period, dosage is increased each week from 8 mg/day toward the target chronic dose of 24 mg/day. The 6 weeks of training will occur once the chronic dose has been established. Arrows indicate evaluation sessions.

As cyproheptadine can have side effects, the dosage is generally titrated over time to the desired chronic daily dose in order to permit accommodation to the drug. This dosing schedule can alleviate the severity of some of the side effects. For this study, both cyproheptadine and the placebo will be titrated in the same manner, beginning at up to 8 mg (up to 4 mg taken 2 times daily) and increasing the next week to up to 16 mg (up to 8 mg taken 2 times daily) and reaching the desired dose level of up to 24 mg per day (up to 8 mg taken 3 times daily) the following week (Fig. 2). If side effects occur at higher doses, but not at lower doses, the subject will be maintained at the highest dose tolerated for the remainder of the treatment phase. Participants will maintain this daily dosage for 6 weeks, during which time training will be performed. After completion of the training period, dosage levels will be reduced back to zero over a two-week period. The drug dosage may be reduced from the target level as recommended by the study doctor.

[figure not shown]

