The hospital pharmacy will dispense the allotment of the study drug to research staff at each change in dosage over the course of the study (5 dispenses). All pills will be encapsulated by the Research Pharmacist so that both cyproheptadine and placebo will be identical in appearance and weight. Only the Research Pharmacist and study Statistician will have the key identifying which drug each subject was given. In this manner all other study personnel, including the PI, and the subjects will remain blinded as to group membership until the study is complete, or the revealing of this information is deemed medically necessary. Each week during the titration period, the subject will come to the Arms and Hands lab to receive his/her weekly allotment of pills from study staff. Examination by the study doctor will occur at baseline, midpoint, and at the end of the study. To monitor type and severity of potential adverse side effects of the medications, the study doctor or a study team member will complete a checklist for each subject weekly. All subjects, even those in the placebo group, will be given this checklist. Adverse side effects will be rated as "none", "moderate", or "severe" based on subject report. If a subject feels unable to

continue the study due to any side effects, she may end her study participation at that time. Transportation can be arranged to convey subjects to and from the Shirley Ryan AbilityLab during this period in order to preclude the need for subjects to drive when they may be experiencing dizziness or somnolence from the medication. Weekly pill counts will be performed to gauge subject compliance with taking the medication. Participants will receive the subsequent allotment of pills at each dosage change.

Once the chronic dosage is attained, therapeutic training will begin for all subjects. The sensorimotor therapy, consisting of 18 one-hour sessions held over 6 weeks, will focus on the impaired upper extremity, particularly the hand.

[figure not shown]

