electrodes (Bagnoli) from EDC and FDS. Subject strength will also be assessed, by having subjects perform maximum voluntary MCP flexion and extension in the same testing jig while the servomotor provides resistance. The EMG data recorded during these isometric contractions will be used to quantify coactivation. Finally, FDS relaxation time will be determined by having the subject create maximal grip force in the jig and then relax upon hearing the termination of an auditory tone, as we have done previously. Both upper extremities may be tested in a subset of participants in order to determine the impact of cyproheptadine on the non-paretic (ipsilesional) side.

Clinical assessments will be performed at the baseline, pretreatment (week 3), mid, post and follow up evaluation sessions by the study research therapist and study team. This battery of assessments includes the GWMFT, FMA, Chedoke McMaster Stroke Assessment – Stage of Hand (CMSA-H), grip and pinch strengths, the Modified Modified Ashworth Scale (MMAS), the Jebsen Hand Function Test, the Nine-Hole Peg Test, the Box and Blocks Test (BBT), and the Semmes Weinstein Monofilament Touch test.

In addition to these neuromechanical measurements, subjects will be evaluated in terms of sleepiness, depression, and weight gain. These are side effects that could dissuade use of the medication. The Epworth Sleepiness Scale (ESS) will be given to subjects at each testing session (Johns, 1991). This instrument consists of a self-assessment of the propensity to doze (ordinal scale, 0-3) during each of 8 activities of daily living (e.g., sitting and talking to someone). We will use the Beck Depression Inventory-II (BDI-II) for assessing depression in our subjects. The BDI-II is a self-report of 21 items rated on an ordinal scale from 0-3 (Beck, et al., 1996). The BDI-II, a revised version of the Beck Depression Inventory (Beck, et al., 1961), was developed to remove possible bias for older adults from the original instrument. Additionally, subjects will be weighed each week to track fluctuations in weight.

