## DATA AND SPECIMEN BANKING: N/A

## DATA AND SPECIMEN MANAGEMENT: N/A

## PROVISIONS TO MONITOR THE DATA TO ENSURE THE SAFETY OF PARTICIPANTS:

A medical monitor will periodically evaluate the data collected regarding harms to determine whether participants remain safe. Findings from the medical monitor will be reported to the IRB during scheduled continuing reviews.

The data monitor will have access to all data collected, including side effects checklists, surveys and untoward events. This information is collected at the evaluation study visits beginning with the medical examination with the study doctor and Baseline evaluation. The data monitor will perform monitoring every 6 months for the first 1-2 years of the study, then annual if no change to the unanticipated adverse effects of this study.

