## **RISKS TO PARTICIPANTS:**

The primary risks for involvement in this study are associated with the pharmacological agent to be tested. Although cyproheptadine hydrochloride itself is not being used or administered differently than the FDA approved method, it is being used for a potentially different outcome, namely reduced unwanted muscle tone following stroke.

Some of the potential side effects of taking cyproheptadine include: diminished mental alertness, drowsiness, dizziness, hallucinations, insomnia, muscle weakness, chest congestion, headache, hypertension, increased appetite, upset stomach, diarrhea, difficulty urinating, vision problems, skin rash and dry mouth, nose, and throat, and convulsions. Although reported clinical experience has not identified differences in responses between the elderly and younger patients, elderly patients should be more cautious of possible risks. These risks may include decreased hepatic, renal or cardiac function.

To minimize these risks, we will begin with low levels of the drug and gradually titrate (increase) up to the optimal target dose for the study, which is still well within the safe level of this drug. Patients will be evaluated weekly and will be able to contact the study doctor at any time with questions or concerns. As a precautionary measure, liver profiles (requiring blood draws) will be run prior to initiation of drug administration and at the end of week 3 (chronic drug dose) to check drug impact on liver function although liver damage is not a known side effect. Following the medical screening, additional labs may be ordered at the discretion of the study doctor. Adverse events, including falls, will be assessed weekly at minimum.

Additionally, the medication may have side effects when combined with other types of drugs and/or alcohol. Some side effects of taking combined drugs may lead to confusion, high blood pressure, high fevers, tremor or muscle rigidity, and increased activity.

The effects of the study drug, cyproheptadine, on human sperm and eggs have not been studied and are therefore unknown. The effects of cyproheptadine in humans have not shown to cause negative conditions in either the mother or the fetus during pregnancy.

However, studies in animals have shown an increased risk of birth defects and fetal hormonal imbalances. The effects of this medication in women who are nursing have been shown to produce hormonal imbalances in the newborn.

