Title: Altering Activation Patterns Post-stroke **NCT:** NCT02418949 **Date:** 6/4/2014

Analysis: Spasticity will be quantified using the MCP angular position and torque data from the trials of imposed MCP rotation [27, 66-68]. Namely, the nominally passive torque curve (recorded during the 10°/s trial) will be subtracted from the total torque curve (recorded during the 300°/s). Mean reflex torque will then be computed from the resulting signal by averaging across a 300-ms period beginning at the end of stretch. The EMG data, normalized by the values recorded during maximum contraction, will be used to confirm that a reflex occurred. The FDS signal must surpass a threshold of 5% of maximal contraction for classification as a spastic stretch reflex and subsequent evaluation. Coactivation during voluntary tasks will be computed from the ratio of normalized EDC/FDS for flexion and FDS/EDC for extension. Values closer to 0 indicate less coactivation. Relaxation time will be estimated as the elapsed time from cessation of the auditory tone to the FDS signal dropping below a threshold level equal to three standard deviations of the resting signal [34]. Active isometric flexion and extension torque will be found by subtracting the initial, passive torque from the peak torque recorded during the respective trials.

Statistical analyses will be employed to assess the effect of cyproheptadine on these outcome measures. We will perform repeated measures analysis of variance (rmANOVA) with the between-subject factor Drug (cyproheptadine, placebo) and the within-subject factor evaluation Session (pre-administration, week 1, week 2, week 3 - see Fig. 1). To test the first hypothesis, addressing efficacy in reducing hyperexcitability, the measures spastic reflex, FDS relaxation time, and coactivation ratio will be used as dependent variables in a MANOVA. Should evidence of a significant effect appear, i.e., a Wilk's lambda value < 0.05, we will perform subsequent post-hoc ANOVAs to test the effects on individual dependent variables. To examine the second hypothesis, regarding loss of strength, separate rmANOVAs will be conducted for extension and flexion strength. Similarly, as we wish to minimize Type II errors for these potentially negative outcomes, separate rmANOVAs will be run for ESS and BDI-II without correction. Normality of the residuals will be tested for these parametric tests and non-parametric tests will be run if normality assumptions are violated.

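### The weekly side-effect checklist has no mild level, so mild effects must be recorded as absent or as moderate, and any severity summary drawn from it is ambiguous

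*Protocol*

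**What the plan says.** The protocol (Procedures Involved) sets out the checklist's purpose and who fills it in: "To monitor type and severity of potential adverse side effects of the medications, the study doctor or a study team member will complete a checklist". This is done every week. It covers every arm: "All subjects, even those in the placebo group, will be given this checklist". The scale is then given in one sentence: "Adverse side effects will be rated as 'none', 'moderate', or 'severe' based on subject report".

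The protocol's section on safety monitoring puts the record to use: "The data monitor will have access to all data collected, including side effects checklists, surveys and untoward events". Risks to Participants adds a second route of capture, "Adverse events, including falls, will be assessed weekly at minimum", with no severity grading stated.

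Other tolerability measures sit outside the checklist. Under Outcome Measures, "subjects will be evaluated in terms of sleepiness, depression, and weight gain"; the first two use the Epworth Sleepiness Scale (ESS) and the Beck Depression Inventory-II (BDI-II), and the third is weekly weighing. In the SAP, "separate rmANOVAs will be run for ESS and BDI-II without correction", and flexion and extension strength are tested separately. The SAP does not mention the checklist.

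**The concern.** A scale that records severity should have a place for the least severe effect that is present. This one moves from none to moderate. Several effects listed under Risks to Participants, such as dry mouth, dizziness and upset stomach, can be mild, and the documents describe no other severity scale for them. The person completing the form, working from the subject's report, has to choose between recording nothing and recording moderate. Two raters, or one rater in two different weeks, may choose differently.

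The titration schedule is intended to let subjects accommodate to the drug and to soften side effects. An effect that eases from moderate to mild, or first appears as mild at a dose step, has no category of its own. What is at stake is how the data monitor reads the severity record, and what a later table of side-effect severity by drug group would mean.

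**Working it through.** **Reading the documents**

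1. Is there a mild grade, a definition of levels, or a placement rule anywhere? None is found in the protocol or the SAP.
2. Does a planned analysis use the grades? No. The SAP's tests cover the hyperexcitability measures, strength, ESS and BDI-II. Study Endpoints in the protocol lists completion time on the Graded Wolf Motor Function Test and grip relaxation time.
3. Does a dose rule use the grades? No. The protocol says "If side effects occur at higher doses, but not at lower doses, the subject will be maintained at the highest dose tolerated", which turns on occurrence and tolerance and cites no checklist rating.
4. Who does use the grades? The data monitor, and anyone who later tabulates the checklists.

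The plan states no figure that depends on the scale, so there is nothing to reproduce.

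**What the recorded rate means**

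Let p be the true proportion with any effect, m the share of those effects that are mild, and c the share of mild effects recorded as moderate. Then

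recorded rate = p × (1 − m + m × c).

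Moderate is the lowest level above none, so this one number is both the recorded any-effect rate and the recorded moderate-or-worse rate. With c = 1 it equals the true any-effect rate. With c = 0 it equals the true moderate-or-worse rate. The documents do not fix c.

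**Illustration under assumed rates**

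Inputs: 50 subjects per drug group (SAP); two-sided α of 0.05. Assumed, because the documents give no rates: p = 0.20 on placebo and 0.45 on drug, with m from 0.25 to 0.75. The calculation is a single two-proportion test, which the plan does not contain:

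power = Φ[(d − 1.96 × se0) / se1], with d = p2 − p1, p̄ = (p1 + p2)/2, se0 = √(2p̄(1 − p̄)/50) and se1 = √((p1(1 − p1) + p2(1 − p2))/50).

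- All effects recorded: d = 0.25, p̄ = 0.325, se0 = 0.0937, se1 = 0.0903. Power = Φ[(0.25 − 0.1836)/0.0903] = Φ(0.735) = 77%.
- Half mild and recorded as none: rates 0.10 and 0.225, d = 0.125, p̄ = 0.1625, se0 = 0.0738, se1 = 0.0727. Power = Φ[(0.125 − 0.1446)/0.0727] = Φ(−0.270) = 39%.

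| Mild share m | Recorded if mild → none (placebo v drug) | Difference | Power | Recorded if mild → moderate |
|---|---|---|---|---|
| 0.25 | 15% v 33.75% | 18.75 points | 59% | 20% v 45%, power 77% |
| 0.50 | 10% v 22.5% | 12.5 points | 39% | 20% v 45%, power 77% |
| 0.75 | 5% v 11.25% | 6.25 points | 21% | 20% v 45%, power 77% |

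In the last column the any-effect comparison is intact and the severity label is wrong: with m = 0.50, moderate-or-worse reads 20% v 45% when the truth is 10% v 22.5%.

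A second assumed set, 20% v 40% with three quarters mild, behaves the same way. Power is 59% with everything recorded and 15.5% when mild is recorded as none (5% v 10%).

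**The case against.** A reader might infer that the trial's safety and tolerability comparison is distorted. The documents do not support that. No between-arm comparison of checklist grades is planned. The planned comparisons of ESS, BDI-II and strength do not use this scale, and the checklist is applied identically in all arms with drug assignment blinded. Identical use does not prevent misclassification, but without rates or a convention neither its direction nor its size can be stated.

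A reader might also take the checklist for the principal side-effect record. The documents do not call it that. Sleepiness, depression and weight have their own measures, liver profiles are drawn, adverse events are assessed weekly, and the study doctor examines subjects at baseline, midpoint and end. Drowsiness and increased appetite are therefore at least partly covered elsewhere. Dry mouth, dizziness and upset stomach have no other severity scale.

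Three further points are fair. Moderate may be read as present but not severe, in which case no effect is lost and only the label is coarse. The checklist form is not in the documents, so it may carry anchors that the protocol omits. And the power figures rest on assumed rates and on 50 completers per group, who are fewer than those dosed if any drop out. All three stand, and they limit how much can be claimed. They do not supply the missing level or the missing convention: the protocol states the scale, and on that scale a mild effect has no place.

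**Conclusion.** The point holds as a limited defect in a safety record. The checklist is meant to capture severity, and its stated scale cannot represent a mild effect. The consequence is confined to the data monitor's review and to any tabulation of severity by drug group, either of which would misclassify mild effects by an amount that the documents do not allow anyone to calculate. The rates and power figures above show only how far the record could move under assumed inputs; they are not estimates for this trial. The primary endpoint, the sample size, the planned tests and the dose rule are untouched. This is a cheap improvement, not a threat to the trial's conclusions.

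**What to change.** Add a mild level to the checklist (none, mild, moderate, severe), with a one-line anchor for each level, and use it at every weekly contact in all arms. State in the SAP how checklist data will be summarised. For subjects rated on the three-level scale, tabulate ratings before and after the change separately, and make any-versus-none the common summary. That summary bridges the two periods only if mild effects were recorded as moderate under the three-level scale, so the convention that raters actually followed should be written down. If the form already has a mild level, correct the protocol sentence to match it.

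The cost is a form change and a minor amendment. The downside is a mid-study change of scale that splits the severity record. The protocol anticipates that enrolment ends in October 2020 and carries an approval stamp from June 2020, so few subjects may be left to benefit. If so, writing down what the existing three levels mean would remove the ambiguity for later ratings without splitting the scale, though mild and moderate would still not be separated.

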### Active Movement Therapy (AMT), VAEDA:

A Voice and EMG-driven Actuated hand orthosis, the VAEDA glove, will be worn by all subjects during these therapy sessions. The VAEDA glove contains cables (Spectra kite wire) which run across the back of the digits in order to provide extension and resist flexion (Fig 3). Forces are transmitted through the cables from a DC micromotor (1724, Faulhaber, Inc), located remotely, to the digits. The single actuator controls torque or displacement in the cable. Tension in the cable is measured directly with a custom tension sensor; cable displacement is estimated from the motor encoder (IE2-16, Faulhaber, Inc.). The cable travels from the actuator through a Bowden cable to a forearm splint, at which point it is attached to the 5 cables running to the digits. Along the digits, the cables traverse through custom plastic blocks, which serve both to guide the cable and to prevent joint hyperextension. The weight of the glove with the cables and cable guides is 2.2 N and the forearm splint is an additional 1.5 N, thereby making the total weight on the arm less than 4 N.

**Fig. 3**. Picture of the VAEDA glove system. Cables run through cable guides on the dorsal side of the glove to facilitate extension and resist unwanted flexion (Left). The cable is driven by a single actuator located remotely on the electronics box which can be worn on the back (Center). EMG signals, which control the glove, are processed by custom amplifiers before being transmitted to the microcontroller (Right).

The VAEDA glove can be controlled with up to 3 channels of EMG. Custom pre-amplifiers process the EMG signals before transmitting the data to the microcontroller (RabbitCore® RCM 4510, Digi International, Inc., Davis, CA). For this study, electrodes will be placed above flexor digitorum superficialis (FDS) and extensor digitorum communis (EDC). Assistance of hand opening can be provided by the VAEDA glove, but only if appropriate EMG activity is detected. For example, the EDC EMG signal must reach a specified threshold before extension assistance will be provided. Similarly, the FDS EMG signal has to surpass a threshold level during hand closing before the user is allowed to flex the digits. Additionally, maximum allowable FDS activity during hand opening and EDC activity during hand closing can be specified to address coactivation issues. Feedback of muscle activity and of opening force provided by the VAEDA glove is available to the user through a custom graphical user interface (Fig. 4). As detection of

[figure not shown]

**Fig. 4**. Graphical user interface for the VAEDA glove. Either the magnitude of EMG signals or the force in the cable can be displayed to provide feedback to the user and/or therapist. Green and yellow bars show the magnitudes of EDC and FDS muscles, respectively. The force graph displays the actual readings from the sensor in real-time. Data recorded during hand opening.

movement intent from EMG for even simple tasks, such as hand opening and closing, can be challenging in stroke survivors with significant impairment, the system also contains a voice recognition system, (VRS), (SR-07 Electronic Express, NY), which can be trained specifically for each user within minutes. The entire device can be worn, with the actuator. VRS. microcontroller. and batteries (Tenergy 7.4V Heavy Duty LIPO, Tenergy Corp Freemont, CA) on the lower back (Fig. 3). Alternatively, they can be placed on a tabletop for a seated user.

